10.17 Appendix 17: PGI-S

The following question asks you about your current overall symptoms.

Please check the box that best describes your current situation.

How would you describe your ITP symptoms during the past week?

	None
	Mild
	Moderate
	Severe
	Very severe

This document cannot be used to support any marketing authorization application and any extensions or variations thereof.

PUBLIC COPY

[figure not shown]
10.18 Appendix 18: PGI-C

[figure not shown]
The following question asks you about your overall symptoms now compared to before starting treatment within this clinical study. Please check the box that best describes your current situation.

How would you describe your current ITP symptoms compared to before you started treatment in this clinical study?

[figure not shown]
	Very much worse
	Much worse
	A little bit worse
	No change
	A little bit improved
	Much improved
	Very much improved

[figure not shown]
PUBLIC COPY
This document cannot be used to support any marketing authorization application and any extensions or variations thereof.

[figure not shown]

This

This

This document cannot be used to support any marketing application and any extensions or variations thereof. PUBLIC COPY

10.21 Appendix 21: Sampson Criteria Questionnaire

Anaphylaxis is highly likely when any of the following 3 criteria is fulfilled (Sampson et al, 2006):

1. Acute onset of an illness (minutes to several hours) with involvement of the skin, mucosal tissue, or both (eg, generalized hives, pruritus or flushing, swollen lips-tongue-uvula)

AND AT LEAST ONE OF THE FOLLOWING

- c. Respiratory compromise (eg, dyspnea, wheeze-bronchospasm, stridor, reduced peak expiratory flow [PEF], hypoxemia)
 - d. Reduced BP or associated symptoms of end-organ dysfunction (eg, hypotonia [collapse], syncope, incontinence)
2. Two or more of the following that occur rapidly after exposure to a likely allergen for that patient (minutes to several hours):
 - a. Involvement of the skin-mucosal tissue (eg, generalized hives, itch-flush, swollen lips-tongue-uvula)
 - b. Respiratory compromise (eg, dyspnea, wheeze-bronchospasm, stridor, reduced PEF, hypoxemia)
 - c. Reduced BP or associated symptoms (eg, hypotonia [collapse], syncope, incontinence)
 - d. Persistent GI symptoms (eg, crampy abdominal pain, vomiting)

Reduced blood pressure after exposure to known allergen for that study participant (minutes to several hours): Systolic BP of less than 90mmHg or greater than 30% decrease from the study participant's Baseline systolic BP value.

10.22 Appendix 22: Management of headaches

Based on current available clinical data, headache is the most commonly reported adverse drug reaction in study participants treated with rozanolixizumab. Study participants should be well informed of this potential adverse drug reaction and should be instructed on how to manage it.

Determination of the severity of headache will be consistent with National Cancer Institute Terminology Criteria for Adverse Events (CTCAE) version 5.0. Severe headache is defined as severe pain limiting self-care activity of daily living (ADL). Self-care ADL refers to bathing, dressing and undressing, feeding self, using the toilet, and taking medications.

In the event of a headache the investigators should take the medical history of previous headaches, concomitant medication, and comorbidities (eg, asthma) into consideration.

Study participants experiencing a moderate, severe and/or serious headache will complete the Headache Questionnaire (Appendix 20, Section 10.20) daily until resolution (eg, the headache becomes nonserious, mild, or is completely resolved, whichever comes first). If the severe and/or serious headache is initially reported at a home visit or during a telephone call, the study participant should be evaluated by a healthcare professional at the study site as soon as possible for further investigations. Study participants should be monitored for signs and symptoms suggestive of central nervous system involvement and evaluated immediately if other causes (eg, meningitis, intracranial bleeding) are suspected. Further neurological workup may be performed (if indicated) at the discretion of the investigator or the treating physician and may include a computed tomography scan, magnetic resonance imaging and/or a lumbar puncture for cerebral spinal fluid collection. In addition, samples for exploratory safety biomarkers should be collected for study participants experiencing severe headache or serious headache when possible. These investigations will be performed to further understand the mechanism of headaches in the study participants.

Treatment must be permanently discontinued if a study participant has a serious headache that is considered related to the IMP in the opinion of the investigator. If a study participant experiences a severe AE of headache that is considered related to the IMP in the opinion of the investigator, the dose of IMP may be reduced or the treatment may be temporarily put on hold. If deemed appropriate by the investigator and agreed upon by the study participant and the sponsor, the study treatment can resume upon the resolution of the severe headache event, at the previous dose or at a lower dose. The benefit and risk of the treatment should be carefully considered prior to reinitiating the IMP. If a study participant experiences a second episode of treatment related severe headache in the opinion of the investigator, the treatment can only be continued upon agreement with the sponsor, investigator, and study participant taking benefit and risk into consideration. If the benefit-risk balance is not acceptable, then the participant must discontinue the IMP. If a participant experiences >2 severe headaches that are considered related to the IMP in the opinion of the investigator, the treatment must be permanently discontinued.

Dosing modifications are allowed if judged necessary by the investigator from [REDACTED] based on specific volume reduction per protocol guidance, provided the treatment is effective as evidenced by relevant efficacy measurements (eg, platelet count $\geq 30 \times 10^9/L$).

Headaches will be treated as clinically indicated according to national guidelines. It is recommended that the study participant has an analgesic available in case of headache with the

instruction for frequency and dosage provided by a health care professional. The analgesic can be started at the early onset of headache. Study participants experiencing any treatment related headache will be followed until resolution of the event.

Prophylactic treatment of headaches may be permitted for study participants who have experienced previous episodes of treatment related moderate or severe headache after discussion with the medical monitor. The benefit risk of continuing treatment with IMP and chronic prophylactic treatment with analgesics must be carefully evaluated by the investigator.

PUBLIC COPY
This document cannot be used to support any marketing authorization application and any extensions or variations thereof.

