7.1.3 Discontinuation of IMP due to other adverse events or medical condition

Study participants **MUST permanently discontinue IMP** and move into the SFU Period if any of the following events occur:

- Study participant has a significant infective episode including but not limited to: bacteremia or sepsis, infectious meningitis, osteomyelitis, septic arthritis, complicated pneumonia or visceral abscess which may or may not result in hospitalization. This list is not intended to be all inclusive, and the investigator is expected to apply his/her judgment on continuing IMP based on the clinical situation at hand (see Appendix 25, Section 10.25).
- Study participant has new onset or recurrent neoplastic disease (except for superficial basal or squamous cell carcinoma of the skin not requiring targeted biological therapy, chemotherapy or radiation).
- Study participant has an AE of severe or serious hypersensitivity, infusion related reaction (see Appendix 24, Section 10.24) or anaphylaxis requiring corticosteroid and/or epinephrine therapy (see Appendix 21, Section 10.21) (Sampson et al, 2006).
- Study participant has a serious AE of headache or GI disturbance that is considered related to the IMP in the opinion of the investigator; or recurrent severe AE of headache (see Appendix 22, Section 10.22) or GI disturbance that is considered related to the IMP in the opinion of the investigator (See Appendix 23, Section 10.23).
- Study participant has a life-threatening bleeding event.
- Study participant has an AE of arterial or venous thromboembolic event (eg stroke, myocardial infarction, pulmonary embolism, deep vein thrombosis).
- Study participant has evidence suggestive of potential TB infection (eg, exposure), and further examinations result in a diagnosis of active TB, LTBI, or NTMBI (see Section 8.2.5).
- If a NTMBI is identified during the study, the same withdrawal procedures as those used for an active TB infection identified during the study should be followed.

Study participants who permanently discontinue IMP during the Treatment Period and hence are withdrawn from the study should complete the assessments outlined for the Early Withdrawal (EW) Visit and enter the SFU Period.

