7.1.4 Temporary IMP discontinuation

Study participant **MUST temporarily discontinue IMP** if any of the following events occur:

1. Thrombocytosis (platelet count of $\geq 400 \times 10^9/L$).

2. In the event of confirmed COVID-19 infection (eg, signs/symptoms such as fever, cough, shortness of breath), or known exposure sufficient to necessitate testing or self-imposed quarantine.

The IMP may be restarted if:

- a. COVID-19 test is negative, and signs and symptoms have resolved
- b. If test is not available, resolution of signs and symptoms and 14 days have passed since initial presentation of the clinical signs/symptoms.
- c. If asymptomatic, 14 days have elapsed since known exposure.

Study participant **MAY temporarily discontinue IMP** if any of the following events occur:

1. A severe AE of headache that is considered related to the IMP in the opinion of the investigator (Section 10.22)
2. A splenectomised study participant develops a (persistent or re-occurring) nonserious infection, as per investigator's decision (Section 10.25)
3. Total serum IgG value is <1g/L as per investigator's decision. As IMP treatment is administered weekly, the decision to temporarily hold the treatment should be determined based on the most recently available total IgG value. As the IgG, IgG subtypes, albumin and total protein levels will be blinded to both the study site personnel and the clinical team at the sponsor and CRO, unblinded Medical Monitors will be monitoring the IgG levels and will alert the investigator in case of decreases <1g/L. Additionally, guidance for investigators on management of infections can be found in Appendix 25, Section 10.25.

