7.2 Participant discontinuation/withdrawal from the study

Study participants are free to withdraw from the study at any time, without prejudice to their continued care. Participants who withdraw from the study should complete the EOS Visit.

A study participant may also be withdrawn from the study at any time at the discretion of the investigator for safety, behavioral, compliance, or administrative reasons.

If the study participant withdraws consent for disclosure of future information, the sponsor may retain and continue to use any data collected before such a withdrawal of consent.

If a study participant withdraws from the study, he/she may request destruction of any samples taken and not tested, and the investigator must document this in the site study records.

See the Schedule of Activities (Section 1.3) for data to be collected at the time of study discontinuation and follow up and for any further evaluations that need to be completed.

Study participants **must** be withdrawn from the study and permanently discontinued from IMP if any of the following events occur:

1. Study participant withdraws his/her consent.
2. Study participant takes prohibited concomitant medications as defined in this protocol.
3. Study participant meets the mandatory IMP discontinuation criteria as per Section 7.1.1, Section 7.1.2 or Section 7.1.3.

4. There is confirmation of a pregnancy during the study, as evidenced by a positive pregnancy test.
5. The sponsor or a regulatory agency requests withdrawal of the study participant.

Study participants who withdraw from the study or permanently discontinue IMP during the Treatment Period should complete the assessments outlined for the EW Visit, enter the SFU Period and complete the EOS Visit.

Investigators should contact the Medical Monitor, whenever possible, to discuss the withdrawal of a participant in advance. Study participants who are withdrawn will not be replaced.

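### For a second severe, IMP-related, non-serious headache, Protocol 7.1.3 and 7.2 on their plain wording require a permanent stop and withdrawal, while Appendix 22 conditionally allows treatment to continue

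*Protocol*

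**What the plan says.** Protocol 7.1.3 lists events after which participants "MUST permanently discontinue IMP". The headache item covers a serious related headache and goes on: "or recurrent severe AE of headache (see Appendix 22, Section 10.22) or GI disturbance that is considered related to the IMP". It gives no number of episodes and no option to continue.

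Protocol 7.2 lists what obliges both withdrawal from the study and permanent discontinuation of IMP. One entry is "Study participant meets the mandatory IMP discontinuation criteria as per Section 7.1.1, Section 7.1.2 or Section 7.1.3".

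Protocol 7.1.4 places a severe related headache among the events for which a temporary hold is optional, and also points to Appendix 22.

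Appendix 22 (Protocol 10.22) sets out a ladder for related headache:

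- Serious headache: permanent stop.
- First severe headache: "the dose of IMP may be reduced or the treatment may be temporarily put on hold".
- Second severe headache: the rule opens "If a study participant experiences a second episode of treatment related severe headache in the opinion of the investigator" and continues "the treatment can only be continued upon agreement with the sponsor, investigator, and study participant taking benefit and risk into consideration". It then adds: "If the benefit-risk balance is not acceptable, then the participant must discontinue the IMP".
- More than two severe headaches: permanent stop, with no discretion.

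**The concern.** In ordinary usage a second episode is a recurrent one. On that reading, 7.1.3 and 7.2 leave a site no choice at the second severe related headache, while Appendix 22 gives it a conditional choice. Two investigators following the same protocol could handle identical participants differently, and each could cite a section in support.

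Three things depend on the answer:

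- **Safety handling.** Appendix 22 calls headache the most commonly reported adverse drug reaction, and Protocol 8.3.8 makes severe headache an event of special monitoring.
- **Classification.** TEAEs leading to withdrawal of IMP are a secondary safety endpoint (Protocol Table 3-1), and SAP 10.2.2 still tabulates TEAEs leading to permanent discontinuation. A TEAE that ends treatment permanently also makes the participant a non-responder for the primary endpoint (Protocol Table 9-1, SAP Table 8-1).
- **Deviations.** Protocol Section 8 rules out waivers, and SAP 5.2 counts departures from the withdrawal criteria among important deviations. A site that followed Appendix 22 could be recorded as having breached 7.1.3 and 7.2.

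**Working it through.** The plan gives no figure to reproduce here. The check is to set the rules side by side for headache judged related to IMP.

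| Event | 7.1.3 and 7.2, plain wording | 7.1.4 | Appendix 22 | Consistent? |
|---|---|---|---|---|
| Serious headache | Permanent stop and withdrawal | Not the governing rule | Permanent stop | Yes |
| First severe, non-serious | Not triggered | Optional hold | Optional dose reduction or hold | Yes |
| Second severe, non-serious | Permanent stop and withdrawal | Optional hold, if each episode is taken alone | Continue if three parties agree; stop if benefit-risk is unacceptable | **No** |
| Third or later severe, non-serious | Permanent stop and withdrawal | Overtaken by 7.1.3 | Permanent stop | Yes |

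The conflict is confined to the third row. Within that row it arises only when the three parties agree to continue, because when benefit-risk is unacceptable both texts lead to a stop.

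The next question is whether the cross-reference settles the matter.

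1. Appendix 22 does not use or define *recurrent*, and neither does any other section in relation to headache.
2. In 7.1.3 the same adjective also introduces severe GI disturbance, which points to Appendix 23. That appendix gives no episode count. If *recurrent* meant more than two for headache, one word would carry two meanings in one sentence.
3. The infection item in 7.1.3 expressly leaves room for the investigator's judgment on continuing. The headache item does not.
4. Section 7.2 imports 7.1.3 as a mandatory criterion and does not mention the Appendix 22 ladder.

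The pointer therefore sends the reader to Appendix 22 without saying that its ladder limits the compulsory rule.

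**Size.** The documents do not give the frequency of a second severe related headache. Protocol 9.8 plans 60 participants on weekly dosing at 2:1, so the active arm is 60 × 2/3 = 40. One participant is 1/40 = 2.5 percentage points of the active-arm discontinuation rate. The responder rate would move by the same amount only if that participant would otherwise have responded. This is an illustration of scale, not an estimate of an effect.

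**The case against.** The best defence is that the two texts are meant to be read together. The pointer to Appendix 22 stands directly after the words for recurrent severe headache, the appendix supplies a graded scheme, and 7.1.4 delegates to it in the same way. The summary of changes shows that 7.1.3 and Appendix 22 were both revised in Amendment 3. On this view 7.1.3 names the category, Appendix 22 says when stopping is compulsory, and 7.2 adds no separate conflict because it only repeats 7.1.3. This is a possible reading and it softens the problem. It does not remove it, because no text states that reading and the plain wording of 7.1.3 says otherwise.

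The defence is also right that the case should be rare. Headache being the most common reaction refers to all grades. Protocol 2.2 reports no severe adverse events after subcutaneous dosing in UP0018 and no severe headache in CIDP01 or TP0001. It does report more frequent and more severe headache on rozanolixizumab in MG0002, without counts.

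Three stronger readings are tempting but not supported:

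- **That Appendix 22 tolerates a second episode freely and stops only after more than two.** It allows continuation only by agreement and compels a stop at that episode when benefit-risk is unacceptable. More than two is the automatic, count-based threshold only.
- **That the size can be read from the 33 participants actually randomized.** The documents give no arm sizes for them, and SAP 1 and 3.2.4 place them under earlier protocol versions, so the wording examined here did not govern them.
- **That the primary result is at risk.** SAP 3.9 drops all formal efficacy testing, so any effect would be on descriptive counts.

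**Conclusion.** The point holds in a narrow form. For the second severe, IMP-related, non-serious headache, the plain wording of 7.1.3 and 7.2 and the ladder in Appendix 22 prescribe different actions, and nothing in the documents says which prevails. This is an inconsistency in a mandatory safety stopping rule that also decides who is counted as a TEAE discontinuation.

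The conclusion rests on reading *recurrent* in its ordinary sense, as including a second episode; a stated definition of more than two would dissolve the conflict. The numerical effect is unknown and probably small. For this trial it is further limited by early termination, by the absence of anyone treated under Amendment 3, and by descriptive reporting. No view is taken here on which clinical rule is right.

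**What to change.** Reconcile Protocol 7.1.3, 7.2 and Appendix 22 so that *recurrent* has one stated meaning and all three sections give the same action at the second episode. The sponsor decides the clinical content. The cost is a few lines of wording in an amendment or a clarification letter to sites.

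Because the trial stopped before anyone was treated under this amendment, the step that still matters for its results is in the clinical study report. It should state which headache stopping rule was in force for the participants enrolled, and that this rule was used when classifying TEAEs leading to permanent discontinuation and any withdrawal-criteria deviations. That costs a sentence or two and needs no further data collection.

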10.23 Appendix 23: Management of diarrhea

Severe (Grade 3) diarrhea is defined as an increase of ≥ 7 stools per day or hospitalization for management of diarrhea or limiting self-care ADL. Determination of the severity of diarrhea will be consistent with CTCAE version 5.0 (see Appendix 3, Section 10.3).

Diarrhea will be treated as clinically indicated according to the local guidelines.

Stool samples may be collected for stool analysis to rule out infection for study participants reporting severe diarrhea. Stool sampling will be done as clinically indicated in the opinion of the investigator and assessed per local guidance. In addition, collection of blood samples for assessment of exploratory safety biomarkers is required for study participants with severe GI disturbances including diarrhea.

In study participants experiencing severe treatment related diarrhea, dosing modifications are allowed, if judged necessary by the investigator, from [REDACTED] based on specific volume reduction per protocol guidance, provided the treatment is effective as evidenced by relevant efficacy measurements (eg, platelet count $\geq 30 \times 10^9/L$).

This document cannot be used to support any marketing authorization application and any extensions or variations thereof.

PUBLIC COPY

10.24 Appendix 24: Management of infusion reactions or hypersensitivity reactions

Study participants must be closely monitored for reactions during and after the IMP administration period. Standard precautions must be taken for the study participants with regard to potential infusion related reactions. Suggested management guidelines for infusion-related reactions and anaphylaxis at the study site are provided in [Table 10-7](#). Definitions of the severity of the relevant events will be consistent with CTCAE version 5.0 (see Appendix 3, Section [10.3](#)). Fully trained healthcare professionals administering the IMP at home should follow their own management guidelines, which should be reviewed and endorsed by the investigator prior to first home administration.

Table 10-7: Suggested management guidelines at the study site for infusion reactions

Type of reaction	Suggested action
Acute – Mild Grade 1	Monitor vital signs every 10 min. If the reaction worsens to Grade 2, follow the instructions below.
Acute – Moderate Grade 2	Interrupt/hold infusion temporarily to further assess and initiate treatment if necessary. Consider the use of iv fluid and antihistamine iv or im. Consider administering paracetamol or NSAIDs. Monitor vital signs initially every 5 min. If the reaction improves and upon further assessment it is clear that the event is not an anaphylaxis, restart the infusion cautiously. Continue to monitor vital signs every 5 minutes. If reaction recurs or worsens to Grade 3, discontinue infusion.
Acute – Severe Grade 3 or anaphylaxis	Discontinue IMP infusion permanently. Alert crash team. Maintain airway; ensure oxygen is available. Administer: 
 – Antihistamine iv/im, corticosteroids iv, epinephrine im, and iv fluids as appropriate. – Monitor vital signs every 2 min. – Hospitalize, if condition not improving or worsens. – Monitor study participant until symptoms resolve.

CTCAE=Common Terminology Criteria for Adverse Events; im=intramuscular; IMP=investigational medicinal product; iv=intravenous(ly); NSAID=nonsteroidal anti-inflammatory drug

Note: Management criteria were adapted from the CTCAE v5.0 (National Cancer Institute, 2017).

In case of suspected anaphylaxis, the Sampson’s Criteria (Sampson et al, 2006) should be accessed and Appendix 21 (Section [10.21](#), Sampson Criteria Questionnaire) should be

completed. The infusion must be discontinued immediately, and emergency resuscitation measures implemented.

In study participants experiencing an infusion-related reaction or anaphylaxis, blood samples will be collected as soon as possible, while the event is ongoing, to investigate the nature of the reaction as per Schedule of Activities (Section 1.3).

Samples for serum complement (C3, C4) and plasma complement (C3a, C5a) should be collected as specified in the Schedule of Activities (Section 1.3). Additional tests such as IgE levels, tryptase may be performed when there is a suspicion of Type I or III hypersensitivity reaction. The results of all monitoring, including laboratory testing, should be made available to the study site and Sponsor.

PUBLIC COPY
This document cannot be used to support any marketing authorization application and any extensions or variations thereof.

